11.5. Restricted Mean Analysis

The common method for describing benefit on the time scale is to calculate the difference in median event time between the 2 treatment arms. An alternative method for describing benefit on the time scale is to estimate the average difference between the K-M curves. This corresponds to calculating the difference in the average time to event for the 2 treatment arms (Irwin 1949; Karrison 1997; Meier et al. 2004). Similar to the HR, this method uses all of the available information across the K-M curves, but has the additional advantage of assessing benefit on the time scale.

To estimate an improvement in OS with pegilodecakin +FOLFOX, we will follow the method of Irwin (1949) detailed in Karrison (1997) and Meier and colleagues (2004) for estimating the 'difference in average OS,' which we will refer to more formally as the restricted mean difference in OS.

The area under each K-M curve will be calculated using numerical integration (trapezium rule) per Karrison and implemented in SAS using PROC LIFETEST. The difference between treatment arms and a CI for the difference will be formed.

Since the K-M curve may be ill-determined beyond a certain range, or even undefined (if the longest observation is censored), for evaluation and comparison of means, the area under each K-M curve will be calculated between time 0 and restriction time T, which is why this is referred to as a "restricted mean." Following the suggestion of Karrison, the restriction time T will be chosen as largest time point t such that the standard error (SE) of the survival estimate at time t in each treatment group is no more than 0.075. For this purpose, we will use the simple, albeit conservative, formula proposed by Peto et al. (1977) for calculating the SE of S(t) as

$$SE(S(t)) = S(t)\sqrt{1 - S(t)/n(t)}$$

, where n(t) is the number of patients still at risk at time t.

12. Safety Analysis

Unless otherwise stated, safety summaries will be produced by actual treatment patient received for the safety population.

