7.3. Sample Size

The sample size is calculated in order to compare the OS between patients randomized to receive pegilodecakin in combination with FOLFOX versus FOLFOX alone. Approximately 566 patients will be randomized to the 2 arms in a 1:1 ratio to observe at least 393 death events. Assuming a median OS time for the FOLFOX arm of 5.9 months, 393 events are needed to detect a 35% increase with 85% power using a log-rank test (2-sided) with an overall type 1 error of 0.05, which corresponds to a median survival of 8 months in the pegilodecakin in combination with FOLFOX arm (hazard ratio [HR] = 0.7375).

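### The formula in SAP 11.5 that fixes the restricted-mean cut-off is, as it reads, not a standard error, and in most trials it would yield no restriction time

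*SAP*

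**What the plan says.** SAP 11.5 adds a restricted mean difference in OS as a time-scale description of benefit, alongside the difference in medians. Each Kaplan-Meier curve is integrated from 0 to a time T, because the curve may be poorly determined further out. The rule is that "the restriction time T will be chosen as largest time point t such that the standard error (SE) of the survival estimate" at that time "in each treatment group is no more than 0.075". The standard error for this purpose is given as S(t) × sqrt(1 − S(t)/n(t)), where "n(t) is the number of patients still at risk at time t".

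The SAP calls the formula simple and conservative and credits it to a 1977 source. That source is not in the reference list in SAP section 15. Section 11.5 gives no alternative formula, no fixed T and no fallback if no time qualifies.

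SAP 11.4 places only PFS and ORR after OS in the testing hierarchy. The restricted mean is not in it.

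**The concern.** A standard error of S(t) must be 0 before any death has occurred and must shrink as more patients are at risk. The expression in 11.5 does neither. It is close to 1 at the start of follow-up and it rises with n(t) towards S(t). A ceiling of 0.075 then no longer limits imprecision. In effect it becomes a requirement that survival has fallen to about 7.5% in both arms.

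If follow-up ends before that happens, the prespecified rule returns nothing. T would then have to be chosen after the curves had been seen, in an open-label trial. That would weaken the one OS contrast in the SAP, apart from medians, that is expressed in time gained.

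**Working it through.** **Inputs.**
- SAP 7.3: "Approximately 566 patients will be randomized to the 2 arms in a 1:1 ratio to observe at least 393 death events", so 283 per arm; "Assuming a median OS time for the FOLFOX arm of 5.9 months"; "which corresponds to a median survival of 8 months in the pegilodecakin in combination with FOLFOX arm (hazard ratio [HR] = 0.7375").
- Protocol 2.3.4: 25 months of enrolment. Neither document gives the accrual shape or a dropout rate, so uniform accrual and no dropout are assumptions here.
- SAP 11.5: the formula and the 0.075 ceiling.

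**Plan's own figure.** SAP 7.3 says "393 events are needed to detect a 35% increase with 85% power using a log-rank test (2-sided) with an overall type 1 error of 0.05". With z = 1.960 + 1.036 and HR 0.7375:
- Schoenfeld: 4z²/(ln HR)² = 388 deaths.
- Freedman: z² × [(1 + HR)/(1 − HR)]² = 394 deaths.

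Both agree with 393, so the design basis is sound.

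**What the formula should look like.** Take a binomial variance S(1 − S)/N with effective size N = n/S. This gives S²(1 − S)/n, so SE = S × sqrt([1 − S]/n). The two forms differ only in what is divided by n.

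| S | n | S × sqrt(1 − S/n) | S × sqrt([1 − S]/n) |
|---|---|---|---|
| 1 | 283 | 0.998 | 0 |
| 0.5 | 283 | 0.4996 | 0.021 |
| 0.5 | 10 | 0.487 | 0.112 |
| 0.075 | 1 | 0.0721 | 0.0721 |

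The first form grows with n and the second shrinks. They coincide only at n = 1.

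**When the ceiling can be met as the formula reads.** S must be about 0.075. Under exponential survival this happens at median × log2(1/0.075) = median × 3.737:
- FOLFOX: 5.9 × 3.737 = 22.0 months.
- Arm 1: 8 × 3.737 = 29.9 months.

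Under the same assumptions the 393rd death comes on average 26.8 months after the first enrolment. Arm 1 therefore does not usually get low enough in time.

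**Simulation.** 566 patients 1:1, exponential OS, data cut at the stated number of deaths. T is the largest observed time with at least 1 patient at risk and the ceiling met in both arms.

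| Scenario | No qualifying T, formula as it reads |
|---|---|
| Planning medians, 393 deaths | about 87% (86–88%) |
| Both medians 5.9 months, 393 deaths | about 56% (52–57%) |
| Both medians 8 months, 393 deaths | 92–94% |
| Planning medians, 276 deaths | about 99% (98–99%) |
| Accrual over 20 months, 393 deaths | 96–98% |
| Accrual over 30 months, 393 deaths | 65–68% |
| Dropout 1% and 3% a month, 393 deaths | 80–82% and 61–64% |

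Other readings of the rule soften the first row a little. It is 84% if a curve that reaches 0 is carried forward, and 78% if T is found per arm and the smaller value taken. Where a T does exist, it sits at about 1 patient per arm.

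**Same simulation with the bracketed form.** T exists in every trial. At 393 deaths its median is about 24.5 months (5–95%: 22 to 26), with a median of 3 at risk in Arm 1 (1–8) and 1 in Arm 2 (1–4).

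**The case against.** **The bracket may have been lost in reading the PDF.** This is the strongest reply. The two forms differ by one grouping, and the same SAP text shows similar damage. The duration formulas in 10.1.1 have no minus sign between the two dates. The 80 kg split appears as ≥ in 6.3 and as > in 10.1.1. This stands as a caveat: the source page decides whether the plan itself is wrong. It does not dispose of the point, because the equation is well formed as it reaches us and nothing else in the SAP supplies the right form. The source that would do so is not in the reference list.

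**The stakes are low.** This stands. OS is tested by the stratified log-rank test and described by hazard ratio, medians and fixed-time survival rates (SAP 11.1). A reader might infer that the primary conclusion or the type I error is at risk. The documents do not support that, since the restricted mean carries no alpha.

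**A reader might also infer that the rule fails even with the right formula**, because T then lands where 1 to 3 patients remain, and that T should be fixed at, say, 18 months. The location is right but the harm is not shown. Under the planning assumptions the corrected rule and a fixed T of 18 months perform alike:
- CI coverage: 93% against 94%.
- Bias: −0.05 against −0.03 months.
- Type I error: 4.5% against 4.8%.
- Power: 83% against 82%.

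The far tail adds little area when survival is near 7.5%. Nor does 11.5 disown that range: the 0.075 ceiling is its own test of what is adequately determined.

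**Conclusion.** The point holds for the formula as it reads. It is not a standard error of S(t), and the rule built on it gives no restriction time in about 87% of trials at the final analysis under the planning medians, uniform 25-month accrual and no dropout. That percentage is not a fixed property of the plan. It is about 56% if both medians are 5.9 months and about 99% at 276 deaths, and it moves with accrual, dropout and the reading of the rule, none of which the documents settle. In every scenario tried, failure is common and no fallback is stated.

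The point is conditional on the source page showing the same equation. It concerns a supplementary description only. It is no ground for replacing the prespecified 0.075 rule.

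**What to change.** Check the equation on the source page of SAP 11.5. If the bracket is missing there, change it to SE(S(t)) = S(t) × sqrt([1 − S(t)]/n(t)), or specify Greenwood's formula, and add the 1977 source to section 15. Keep the 0.075 ceiling and the rest of the rule. With the corrected formula a T was found in every simulated trial, so the gap left by the missing fallback largely closes.

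Optionally, note that T will probably fall in the far tail, with about 3 and 1 patients at risk at the final analysis. A fixed T is not required. At 18 months the expected difference would be about 1.6 rather than 2.1 months, with no gain in power.

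The cost is one line of SAP text. Sample size, data collection, the primary test and the alpha allocation do not change.

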12.1. Adverse Events

Adverse event terms will be coded using the latest version of MedDRA (version 19.0 or later). Adverse events (AEs) will be graded according to the National Cancer Institute (NCI) Common Terminology Criteria for Adverse Events (CTCAE) v4.03.

Summaries of AEs will be generated for those events that are considered treatment emergent, where a TEAE is defined as an AE that begins or worsens in grade after the date of first study drug administration through 30 days after all treatment discontinuation. Any related serious adverse event (SAE) which occurs more than 30 days after all treatment discontinuation will also be considered as TEAE.

All AE data will be presented in listings; separate listings for serious AEs, AEs leading to any study treatment discontinuation (either FOLFOX or Pegilodecakin), and AEs leading to death will be generated. Adverse events by subgroup (age, gender, and race) will also be summarized.

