7.6.2 Adverse Events

Adverse events will be analyzed in terms of TEAEs defined to be any AEs that begin or worsen in intensity after study drug initiation through 30 days after EOT or any treatment-related SAE that occurred any time during the study. All AEs will be coded based on the Medical Dictionary for Regulatory Activities (MedDRA) preferred terms.

All TEAEs due to any cause, drug-related TEAEs, TE-SAEs, drug-related TE-SAEs, and TEAEs leading to discontinuation from the study treatments will be tabulated using the worst grade per NCI CTCAE v4.03 criteria by system organ class and preferred term. Additional summaries include AEs by intensity (Grade 1–4).

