9.4 Reporting of Adverse Events

After the ICF is signed, study site personnel will record via eCRF the occurrence and nature of each patient's preexisting conditions, including clinically significant signs and symptoms of the disease under treatment in the study. In addition, study site personnel will record via eCRF any change in the preexisting conditions and any new conditions as AEs. Investigators should record their assessment of the potential relatedness of each AE to study treatment via eCRF.

At each visit assessment, all AEs either observed by the Investigator or one of the Investigator's professional collaborators, or reported by the patient spontaneously, or in response to a direct question will be recorded on the AEs eCRF, whether believed by the Investigator to be related or unrelated to the study medication. If any AE occurs after dosing with study medication, the patient should be followed with the appropriate treatment and close medical supervision. The AEs that started after signing the ICF and up to 30 days after the last dose of study drug(s) will be collected. The Investigator will record the AE on the CRF and will provide the date of onset, severity,

relationship to study medication, date of resolution (or the fact that it is still continuing), action taken, and outcome of the AE. A causality assessment will be made to determine whether or not the AE is thought to be drug related. Removal of a patient from the study because of AEs or changes in laboratory test values, whether by the Investigator or by the patient's own volition, should be reported to Lilly or designee promptly. Study site personnel must report any treatment discontinuations that result from AEs to Lilly or its designee via eCRF, clarifying, if possible, the circumstances leading to the discontinuation of treatment.

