7.2. Definitions and Conventions

The **date of randomization** is the date the patient was randomly assigned to pegilodecakin + FOLFOX arm or FOLFOX arm using the IVRS.

The **date of first dose** is the date of the first dose of pegilodecakin or any component of FOLFOX whichever is earliest.

The **baseline value assessment** for safety **in general** is the last value observed on or prior to the first dose of pegilodecakin or FOLFOX. For efficacy, the baseline value assessment is the last

value on or prior to the randomization date or the first value on or prior to the first dose of pegilodecakin or FOLFOX whichever occurs earlier.

The change from baseline will be calculated by subtracting the baseline values from the individual post-treatment values. If either the baseline or post-treatment value is missing, the change from baseline is set to missing.

The study day of a safety event or assessment will be calculated as:

- The difference between the date of the event or assessment and the date of first dose plus 1 for all events or assessments occurring on or after the day of first dose. For example, if an event occurs on 08 June 2014 and the date of first dose was 06 June 2014, the study day of the event is 3.
- The difference between the date of the event or assessment and the date of first dose for all events or assessments occurring before the day of first dose. For example, if an event occurs on 05 June 2014 and the date of first dose was 06 June 2014, the study day of the event is -1.

The study day of an efficacy event or assessment will be calculated as:

- the difference between the date of the event or assessment and the date of randomization plus 1 for all events or assessments occurring on or after the date of randomization
- the difference between the date of the event or assessment and the date of randomization for all events or assessments occurring before the date of randomization.

One month = 30.4375 days

One year = 365.25 days

Unless otherwise noted, summaries of continuous variables will include a mean, median, standard deviation, minimum, and maximum.

Unless otherwise noted, summaries of categorical variables will include the frequency and percentage (relative to the population being analyzed) of each category.

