10.1. Concomitant Medications

Concomitant medications will be coded using the most recent version of World Health Organization (WHO) Drug Dictionary. Concomitant medications are defined as

- The medication was started on or after the date of first dose of study treatment and before treatment discontinuation date + 30day;
- The medication was started prior to first dose study treatment but was ongoing at the time of the first dose of study treatment.

Concomitant medications will be summarized separately and presented by drug class and PT by randomized arm on safety population. In addition use of selected concomitant medication, such as steroid, use will be summarized separately. Study Treatments

All study treatment summaries will be based on the Safety population.

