12.8. Utilization

Utilization data will be summarized by category across arms. The following categories will be described:

- transfusions (on study treatment and within 30 days after the treatment discontinuation)
- growth factor
- hospitalizations (on study treatment and within 30 days after the treatment discontinuation)
- post discontinuation systemic therapy

For categorical variables, frequency and the corresponding proportions will be summarized by treatment arm.

13. Pharmacokinetics

Pegilodecakin observed concentrations will be summarized by descriptive statistics.

Additional analysis utilizing the population PK approach may also be conducted if deemed appropriate. Relationships between pegilodecakin exposure and measures of efficacy and safety may be explored.

A separate analysis plan for pegilodecakin PK and exposure/response will be provided.

14. Immunogenicity

The treatment-emergent anti-drug antibody (TE ADA) evaluable population will be defined within the Safety Population as those patients with both a baseline ADA test result and a postbaseline ADA test result. As a proportion of the TE ADA evaluable population, the number and frequency of the following will be tabulated by treatment group: TE ADA+ patients, and TE ADA+ patients with detected higher-tier assay results. Included in the same tabulation will be, as a proportion of the TE ADA evaluable population, the number and frequency of patients with ADA present at baseline, as well as patients with detected higher-tier assay results at baseline.

A summary will be provided of the number and percentage of patients who receive pegilodecakin reporting specific TEAEs (overall and by PT) by patient TE ADA status (TE ADA+, TE ADA-, TE ADA Inconclusive, Patient not evaluable for TE ADA). The PT will be ordered by decreasing frequency in the TE ADA+ status group. The specific TEAE of interest are events in any one of the MedDRA Anaphylactic reactions Standardized MedDRA Query (SMQ), Hypersensitivity SMQ, Angioedema SMQ, Injection site reactions High Level Term (HLT), or Infusion site reactions HLT.

Additional immunogenicity analyses, to be presented in a standalone immunogenicity report in context with other studies of pegilodecakin, will be described in a separate SAP.

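### SAP 12.1 opens the treatment-emergent window the day after first dose, so Cycle 1 Day 1 adverse events that never worsen later fall outside the TEAE summaries

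*SAP*

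**What the plan says.** SAP 12.1 says that AE summaries are produced for treatment-emergent events, and that "a TEAE is defined as an AE that begins or worsens in grade after the date of first study drug administration". The window closes 30 days after all treatment has stopped. The one stated addition is a related SAE occurring later than that.

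The first-dose date is a calendar date. SAP 7.2 says it "is the date of the first dose of pegilodecakin or any component of FOLFOX whichever is earliest".

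Protocol 7.6.2 uses a different start and counts "any AEs that begin or worsen in intensity after study drug initiation". The protocol synopsis, under safety analyses, uses a third: onset or worsening after randomization.

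Elsewhere the SAP includes the first-dose date explicitly. In 7.2, safety study day is the difference between the event date and "the date of first dose plus 1 for all events or assessments occurring on or after the day of first dose". In 10.1, the first limb of the concomitant-medication definition reads "The medication was started on or after the date of first dose of study treatment".

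On data collection, Protocol 9.4 says the investigator "will record the AE on the CRF and will provide the date of onset", along with severity, relationship and outcome. It does not mention an onset time.

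SAP Section 14 carries the definition forward into a table by ADA status: "The specific TEAE of interest are events in any one of the MedDRA Anaphylactic reactions Standardized MedDRA Query", followed by the hypersensitivity, angioedema, injection-site and infusion-site groupings.

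**The concern.** Comparing safety and tolerability between arms is a secondary objective. Cycle 1 Day 1 is the first exposure to study drug: Arm 1 receives its first AM0010 injection and then FOLFOX (Protocol 5.1.3), and Arm 2 its first FOLFOX. A rule that requires onset after the date of first administration leaves that day out.

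The events most exposed are short-lived ones that begin on the day of dosing and resolve without getting worse, which is how a brief acute reaction would behave. The omission need not be equal between arms, because a reaction to the first AM0010 injection can occur only in Arm 1.

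**Working it through.** This is a question of definition. It depends on no sample size, event count or alpha level, so the check applies the rules to dates.

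**Reproducing the SAP's example.** SAP 7.2 takes a first dose on 06 June 2014 and an event on 08 June 2014. Study day = event date − first-dose date + 1 = 8 − 6 + 1 = 3, which matches the SAP's stated value of 3.

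**Applying the SAP 12.1 rule to the same patient.** The literal condition is onset (or worsening) date > first-dose date.

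- Onset on 06 June: study day = 6 − 6 + 1 = 1. Is 06 June later than 06 June? No, so it is not a TEAE.
- Onset on 07 June: study day = 7 − 6 + 1 = 2. Is 07 June later than 06 June? Yes, so it is a TEAE.

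The window therefore opens on study day 2.

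**The three definitions side by side**, for an event after randomization:

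| Event | SAP 12.1, literal | Protocol 7.6.2 | Synopsis |
|---|---|---|---|
| Starts before the first dose, no later worsening | No | No | Yes |
| Starts on the first-dose date after dosing, no later worsening | **No** | Yes | Yes |
| Starts on the first-dose date after dosing, worsens on a later date | Yes | Yes | Yes |
| Starts the day after first dose | Yes | Yes | Yes |

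The SAP is alone in excluding the second row. Drug initiation, the protocol's start point, is an event rather than a date, so a reaction following the dose on Day 1 qualifies there. The synopsis goes the other way and also admits events between randomization and dosing, an interval of up to 3 days under Protocol 6.2.

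**Does anything in SAP 12.1 restore Day 1?** The added clause covers only related SAEs more than 30 days after discontinuation. The worsening limb rescues a Day 1 event only if its grade rises on a later date.

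**Which outputs inherit the rule?** The TEAE overview and the preferred-term, system-organ-class and maximum-grade TEAE tables (12.1.1), their drug-related repeats (12.1.2), TEAEs leading to discontinuation (12.1.3), and the Section 14 table by ADA status.

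**With the first-dose date included**, the 06 June onset satisfies 06 June ≥ 06 June and the window opens on study day 1.

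**The case against.** The best reply is that this is loose drafting. Protocol 7.6.2 plainly includes post-dose Day 1 events, SAP 7.2 makes the first-dose date study day 1, and nothing in either document suggests an intention to drop that day. SAP 7.6 places further data-handling rules in a separate programming specification, which may do the sensible thing. It could also be said that AM0010 administration times are recorded, and that silence in Protocol 9.4 does not prove the eCRF lacks an onset time.

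These points bear on what would actually be programmed, which cannot be known from the documents. They do not remove the conflict in the text. The SAP is the governing definition, and it includes the first-dose date expressly in two other places.

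The other side is right to limit the consequences. A reader might infer that all Day 1 events vanish from every TEAE table; they do not, because those that later worsen in grade still qualify. A reader might also infer that a Day 1 anaphylactic reaction would be visible only in a listing. That is not established: the SAE summary in 12.1.1 is not labelled treatment-emergent, although the opening of 12.1 and the protocol's reference to treatment-emergent SAEs leave its filter unclear. Immune-mediated events (12.1.6) and events of special interest (12.1.7) are not expressly limited to TEAEs, deaths are summarised on the ITT population (12.1.4), and reasons for stopping each drug are tabulated separately (8.1). Finally, the Section 14 table relates reactions to ADA status in patients given pegilodecakin. It is affected, but it is not a general display of first-dose reactions.

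**Conclusion.** The definition is wrong as written and should be corrected. Followed literally, SAP 12.1 omits from the TEAE summaries any AE that begins on the date of first dose and does not worsen on a later date, contrary to Protocol 7.6.2, the synopsis and the SAP's own conventions.

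The reach is limited to descriptive safety summaries and to study day 1. The primary endpoint and the hypothesis tests are untouched, and every AE remains in the listings. The number of events cannot be given: neither document reports a Day 1 event rate, and any count built on an assumed rate would also have to guess how many such events worsen later.

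The conclusion rests on reading the SAP wording literally and on the programming specification not overriding it. If that specification already includes Day 1, the SAP text still needs to be changed to match.

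**What to change.** In SAP 12.1, define a TEAE as an AE that starts or increases in grade on or after the date of first dose of any study drug. Exclude a same-day event only if it is recorded as starting before the first dose, and treat unknown timing as treatment-emergent. A pre-dose/post-dose flag or an onset time for Day 1 events would make that rule workable if the eCRF does not already hold one.

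Use the same start point in the protocol synopsis, Protocol 7.6.2 and SAP 12.1. While aligning them, keep the clause that counts related SAEs occurring beyond the 30-day window; a bare 30-day cut-off would remove events that both Protocol 7.6.2 and SAP 12.1 deliberately retain.

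The cost is a wording change and one line of programming. The downside is that a few events which began on Day 1 before dosing may be counted as treatment-emergent, which is the cautious direction for a safety summary.
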